5.7.7. Severe Pneumonia Descriptive Statistics

Further characterization of the severe pneumonias may be performed using descriptive statistics. Each severe CAP or HAP will be described using ICD-10 codes, primary vs. secondary cause, and length of stay in hospital. Reasons for primary admission will be described when pneumonia is a secondary cause. Pneumonia that did not result in hospitalization will be described according to medical codes.

If sample size allows, additional descriptive analysis or modeling among patients who are hospitalized for pneumonia will be performed to better understand if there are patient characteristics that could explain who may have more severe within-hospital pneumonia in terms of longer length of stay, fatality, etc.

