5.3. Data

This study will use the Clinical Practice Research Datalink's (CRPD)-GP OnLine Database (GOLD), a primary care research database in the United Kingdom. We will also include the following data with linkages to CPRD-GOLD:

- Hospital Episode Statistics through August, 2011 (http://www.hesonline.nhs.uk/Ease/servlet/ContentServer?siteID=1937&categoryID =289)
- Office of National Statistics Mortality File or CPRD mortality information through March, 2011 (http://www.ons.gov.uk/ons/rel/subnational-health1/the-21st-century-mortality-files/2010/index.html) [Note: If we do not get access to ONS, we would use CPRD-GOLD algorithms for death in addition to the HES discharge status.]
- Townsend Deprivation Scores (http://www.communities.gov.uk/documents/communities/pdf/733520.pdf)

CPRD-GOLD data were formally referred to as the General Practice Research Database (GPRD). To prevent confusion between the database and the Global Initiative for Chronic Obstructive Lung Disease (GOLD), which characterizes COPD severity and treatment guidelines, the protocol refers to the database as CPRD-GOLD. CPRD-GOLD contains computerized health care information entered by General Practitioners in the United Kingdom (UK). More than 600 General Practices have been contributing medical history data since 1987, with more than 6 million patients in the database. The database contains longitudinal data recorded by the GP on patient demographic and clinical characteristics, medical history including records of referrals to consultants and hospitalizations, primary care utilization, and prescription medication history over a period of up to 15 years. Descriptive and pharmacoepidemiological studies of patients with COPD have been conducted in CPRD-GOLD, including validation of physicianrecorded COPD diagnosis [Soriano, 2001] and evaluation of COPD co-morbidities [Soriano, 2005]. Studies of pneumonia have also been conducted, including a study of CAP in CPRD-GOLD [Müllerova, 2012] and a validation study of CAP requiring hospitalization in The Health Improvement Network (THIN), which uses the same software as CPRD to capture primary care information [Meropol, 2012].

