5.4.3. Pneumonia Definitions

Several pneumonia outcomes will be defined for this study based on what is recorded in HES and/or the GP record. Distinctions will be made between episodes of severe and non-severe pneumonia events as follows:

- Non-Severe CAP
- Severe pneumonia
 - Severe CAP (CAP requiring hospitalization or resulting in death)
 - Hospital-acquired pneumonia (HAP)

These are defined below. The above categories identify three main classification categories of pneumonia that differ in etiology, severity, and prognosis.

CAP episodes will be identified and classified as severe (requiring hospitalization) or non-severe.

CAP will be based on definitions used previously in CPRD-GOLD [Müllerova, 2012] and those published by others [Meropol, 2012], which have undergone extensive review and evaluation. For this study, a more specific definition will be applied to allow inclusion of only those pneumonia events (versus influenza or other respiratory infection) that occur in the community. As a secondary analysis, the more sensitive definition would be used in sensitivity analysis.

Non-Severe CAP will be classified as an episode of pneumonia that was treated in the community and did not result in hospitalization or death. It would be tabulated based on examining pneumonia episodes and subtracting away any severe CAP or HAP.

Severe CAP will be classified based on hospitalization or death due to pneumonia during the CAP episode. The following CAP would be considered as serious:

- Pneumonia episode that do not involve hospitalization and patient dies during the episode (CPRD-GOLD) OR
- Pneumonia episode that results in hospitalization, where pneumonia was recorded prior to hospitalization (CPRD-GOLD) or within the first 2 days of admission to hospital (HES). If recorded in HES, pneumonia could be recorded on any episode within a spell in any position (e.g., primary or secondary).

The codes denoting pneumonia include all ICD-10 codes for Influenza and pneumonia (J09 to J18) except J09, J10.1, J10.8, J11.1, and J11.8:

In HES, spells represent an admission to the hospital and are comprised of a series of care episodes. Each care episode has a primary diagnosis and secondary diagnosis, where the secondary diagnoses are a series of significant co-morbid conditions. Most hospital

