COPD severity	Dx but spirometry conflicts (no COPD)				
	Gold 0 (reference)				
	Ι				
	II				
	III				
	IV				
	Unknown				
Influenza Vaccin	nation (past 12 mo) Yes				
Pneumococcal va	accination (past 5 years.) Yes				
BMI	Underweight (<18.5),				
	Low Normal (18.5 - ≤20.9)				
	High Normal (21-≤24.9)				
	Overweight (25.0 - ≤29.9)				
	Obese (>30.0)				
	Underweight (<18.5),				
Comorbid condi	tions prior to new use				
No is reference for	or each condition				
	Asthma				
	Myocardial Infarction				
	Congestive Heart Failure				
	CerebroVascular Disease				
	Dementia				
	GERD				
	Peptic Ulcer				
	Peripheral Vascular Disease				
	Mild Liver Disease				

		Odds Ratio		
Stratum	Value	Adjusted OR	Lower 95% CI	Upper 95% CI
	Moderate Liver Disease			
	Connective Tissue Disorder			
	Hemiplegia/Paraplegia			
	Diabetes			
	Diabetes (with complications)			
	Anxiety			
	Depression			
	Cancer (non-metastatic solid			
	tumours,			
	leukemias/lymphomas)			
	Cancer (metastatic solid			
	tumours)			
	Lung cancer			
	Renal diseases			
COPD therapy,	past 12 mo associated with			
severity / frailty	(%)			
	Frequent Oral Corticosteroids			
	Home Oxygen therapy			
	Nebulized therapy			
Other COPD th	erapy in prior 12 (%)			
	SABD			
	Theophylline			
Other				
Medications	ACE-inhibitors			
	Statins			
	Immunosuppresants			
	Cancer treatment			
All GP visits wit	thin past 12 mo			
	0			
	1-5			
	6-10			
	11-15, 16-20, >20			
All Emergency Hospitalizations, past 12 mo				
	0			
	1-2			
	3+			
All Non-Emerge	ency Hospitalizations, past 12 mo			
	0			
	1-2			
	3+			

		Odds Ratio			
Stratum	Value	Adjusted OR	Lower 95% CI	Upper 95% CI	
COPD exacerb	COPD exacerbations, past 12 mo				
	COPD hospitalisations				
	0				
	1				
	2+				
	Moderate exacerbations				
	0				
	1				
	2+				

1. Note: This table may be repeated for All pneumonia vs. No pneumonia.

2. The number of covariates will be adjusted based on the number that can be supported by the number of events.

Figures

- 1. Consort Diagram for new user cohort to final analysis population (how many are lost/retained with each inclusion/exclusion including additional requirements for final analysis population
- 2. Time to severe pneumonia (by ICS-containing vs. LABD)
- 3. Time to all pneumonia (by ICS containing vs. LABD)

4. Length of Stay boxplots for hospitalized pneumonia (Severe CAP and HAP combined)

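### Length of stay is read as severity and pooled over all hospitalised severe pneumonia without separating in-hospital deaths, so early deaths count as short stays

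*Protocol*

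**What the plan says.** Section 5.7.7 opens with optional work: "Further characterization of the severe pneumonias may be performed using descriptive statistics". Within it, "Each severe CAP or HAP will be described using ICD-10 codes, primary vs. secondary cause, and length of stay in hospital". Events without an admission are handled differently: "Pneumonia that did not result in hospitalization will be described according to medical codes".

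The next paragraph is conditional: "If sample size allows, additional descriptive analysis or modeling among patients who are hospitalized for pneumonia will be performed". Its aim is to find patient characteristics that explain "who may have more severe within-hospital pneumonia in terms of longer length of stay, fatality, etc". That sentence fixes the direction of reading, since longer means more severe, and it names fatality as a further measure.

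Item 4 in the list of figures at the end of Section 8 reads "Length of Stay boxplots for hospitalized pneumonia (Severe CAP and HAP combined". It has no split by how the stay ended.

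Deaths belong to the severe group by definition (Section 5.4.3): "Severe CAP will be classified based on hospitalization or death due to pneumonia during the CAP episode". Section 5.3 calls mortality an important competing risk, and Section 5.7.4 lists death as a competing cause in the Cox analysis. Neither idea is carried over to length of stay.

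**The concern.** A hospital stay ends in one of two ways, discharge alive or death. If both are recorded simply as days in hospital, a patient who dies on day 2 contributes two days. Under the reading in Section 5.7.7 that ranks as mild disease, although it is the worst outcome. A characteristic that raises early death and leaves recovery unchanged would then go with shorter stays.

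The same characteristic would also show higher fatality, so the two severity measures named in one sentence would point in opposite directions. Length of stay has its own planned figure. No table shell or figure in Section 8 shows in-hospital fatality among the pneumonia cases, and the deaths described in Section 5.7.5 are counted by treatment group only. A reader of Figure 4 would have nothing beside it to correct the impression.

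**Working it through.** The protocol states no length-of-stay or in-hospital fatality figure, so there is nothing to reproduce. The check is of direction and possible size. The inputs are assumed except the event count.

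**Inputs**
- Severe first events: 106 severe CAP + 1 HAP = 107 (Section 5.4.1, Table 4). This is an upper limit for Figure 4, because severe CAP includes deaths without admission.
- Assumed: baseline in-hospital fatality of 5% to 30%; a characteristic that doubles the death hazard or the fatality.

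**Illustration 1: constant daily hazards.** Let d = 0.1 per day be the discharge hazard (assumed) and h the death hazard. Then fatality p = h/(d + h), so h = d × p/(1 − p), and mean stay = 1/(d + h).

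| Baseline fatality | h, then 2h | Mean stay (days) | Ratio | New fatality |
|---|---|---|---|---|
| 5% | 0.0053, 0.0105 | 9.50 to 9.05 | 0.95 | 10% |
| 10% | 0.0111, 0.0222 | 9.00 to 8.18 | 0.91 | 18% |
| 20% | 0.0250, 0.0500 | 8.00 to 6.67 | 0.83 | 33% |
| 30% | 0.0429, 0.0857 | 7.00 to 5.38 | 0.77 | 46% |

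The falls at 10%, 20% and 30% are 9%, 17% and 23%.

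**What would cancel it.** If the characteristic also slows discharge, mean stay is unchanged when the discharge hazard ratio equals (d + h − 2h)/d = 1 − h/d. That is 0.95, 0.89 and 0.75 at baseline fatality of 5%, 10% and 20%. A larger slowing makes the observed stay longer.

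**Illustration 2: early deaths, on the median, as a boxplot shows it.** Assume deaths uniform over days 0.5 to 4, and survivors' stay lognormal with median 8 days and log-SD 0.8. When the median m lies above 4 days it solves p + (1 − p) × Φ(ln(m/8)/0.8) = 0.5.
- p = 10%: Φ = 0.4/0.9 = 0.444, z = −0.140, m = 8 × exp(−0.112) = 7.2 days.
- p = 20%: Φ = 0.3/0.8 = 0.375, z = −0.319, m = 8 × exp(−0.255) = 6.2 days.

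Doubling fatality from 10% to 20% therefore moves the pooled median from 7.2 to 6.2 days, while survivors stay at 8.0 in both groups. By simulation, 5% to 10% gives 7.6 to 7.2 days, and 20% to 40% gives 6.2 to 3.9.

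If survivors' stay is also 25% longer, the 10% to 20% case rises from 7.2 to 7.7 days. In that case the offset is complete when survivors' stay is about 7.15/6.20 = 1.15 times as long.

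**A limit on the simple split.** In illustration 2 the split recovers the right answer, 8.0 against 8.0 days. In illustration 1 it does not. With constant hazards, time to discharge among those discharged alive has the same distribution as total stay, so their mean falls by the same 9%, 17% or 23%. What stays unchanged there is the discharge hazard itself (ratio 1), while the probability of leaving alive falls, for example from 90% to 82%. This is why the death count must stand beside the split, and why any model needs death as a competing event.

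**The case against.** The strongest reply is that the sentence on severity already lists fatality beside length of stay. A characteristic that raises early death would show there, so a reader who infers that it would simply pass for milder disease goes further than the text allows. That is right, and it limits the harm. It does not repair the length-of-stay result, which would still move the wrong way.

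Second, the protocol never says that in-hospital deaths are included. That is so; inclusion is the plain reading of a figure covering all hospitalised severe events, not a stated rule. An analysis plan that is not shown may settle it. The unsplit figure and the direction of the severity reading are, however, stated in the protocol.

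Third, nothing firm is planned: the description is optional, the modelling depends on sample size, and no length-of-stay model is fixed. This stands. A reader might infer that the protocol commits to regressing raw days in hospital on patient characteristics, but it does not.

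Fourth, a boxplot of actual stay reports days in hospital correctly. As a measure of bed use it is not wrong. The difficulty arises only when longer is read as more severe.

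Finally, it might be inferred that a characteristic which raises death must shorten observed stay. The working shows otherwise: modestly slower recovery can cancel or reverse the effect. Early deaths still pull the pooled stay down.

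**Conclusion.** The point holds as a minor one. Section 5.7.7 reads longer stay as more severe, Figure 4 pools all hospitalised severe events, and in-hospital deaths are nowhere separated. Followed as written, early deaths count as short stays, and a characteristic that raises early death can appear to shorten stay unless it slows recovery enough to offset this.

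The possible size depends on fatality, which the protocol does not give. The reductions of 9%, 17% and 23% in mean stay, and the fall in median from 7.2 to 6.2 days, are illustrations on assumed fatality and assumed distributions of stay. They are not estimates for this cohort.

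The analysis is exploratory, rests on at most 107 severe events, and concerns none of the four objectives in Section 4 directly. The primary Cox analysis of severe pneumonia is unaffected.

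**What to change.** In the Section 5.7.7 text and in Figure 4, show length of stay separately for patients discharged alive and for those who died in hospital, with the number and percentage of in-hospital deaths alongside. Suggested wording: *Length of stay will be summarised separately by discharge status, and the number of in-hospital deaths will be given with each summary. If length of stay is modelled, the outcome will be time to discharge alive, with in-hospital death as a competing event.* The stay of patients discharged alive should not be shown without the death count, because it conditions on survival.

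No new data are needed. Section 5.3 plans linked mortality data, and if those are not obtained it says "we would use CPRD-GOLD algorithms for death in addition to the HES discharge status". Either source can identify the deaths.

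The cost is a little more programming and a thin death group. With at most 107 events, an assumed fatality of 10% or 20% gives at most about 11 (0.10 × 107 = 10.7) or 21 (0.20 × 107 = 21.4) deaths. That group may be better listed or shown as individual points than as a box.

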5.7.8. Estimates of Precision

Estimates of precision were calculated on the expanded cohort including new users from the 2002-2010 study period, which included 12,000 ICS-containing medication users and 6,600 LABD users who experienced 283 first pneumonia events, including 106 severe

pneumonia events. Based on the number of pneumonia events prior to censoring, fixed sample size of new users, and rates of pneumonia in the combined population, this study should be able to exclude a margin of 2.0 for severe pneumonia and 1.5 for overall pneumonia.

Rates of pneumonia for the pooled new user cohort were: 15.8 per 1000 PY for CAP, 5.3 per 1000 person years for severe CAP. This was lower than the 22.4 per 1000 person years observed in a prevalent COPD cohort [Müllerova, 2012], but this is plausible as new users would not include as high a proportion of patients with more severe COPD

As part of the additional feasibility analysis, sample size calculations were tabulated to determine the differences that could be detected assuming the rates of CAP in the LABD control arm as 11 per 1000 PY, an odds ratio of 1.5 could be detected assuming a two-sided significance test at the 0.05 level with 85% power: (This would require a rate of 16.4 per 1000 PY and 270 pneumonia events.)

Assuming 5.3 per 1000 PY for severe CAP in the overall new user cohort, if the rate of severe pneumonia is 4 per 1000 PY in the LABD control arm, an odds ratio of 1.85 could be detected assuming a two-sided test at the 0.05 significance level with 82% power. (This would require a rate of 7.4 per 1000 PY in the ICS-containing group for a total of 115 pneumonia events.)

Although ruling out a 20 to 40% margin is desirable for most events, ruling out a margin between approximately 1.5 to 2.0 for overall CAP and severe CAP is still clinically relevant for rare but severe adverse events.

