1. INTRODUCTION

An association has been observed between pneumonia and currently marketed ICScontaining medications relative to non-steroid containing medications among patients with COPD [Ernst, 2007, Crim, 2009; Drummond, 2008; Spencer, 2011; Singh, 2010]. The risk factors for development of pneumonia, including serious pneumonia requiring hospitalization, have been well-characterized in clinical and observational studies and include older age, current smoking, low BMI, certain chronic co morbid conditions (e.g. dementia), higher levels of dyspnoea, and markers of COPD disease severity [Calverley, 2011; Crim, 2009; Mannino, 2009; Müllerova, 2012].

In clinical trials, serious pneumonia was defined as any pneumonia that resulted in death, immediate risk of death (investigator judgment), or hospitalization or prolonged existing hospitalization. In the fluticasone furoate (FF)/vilanterol (VI), an increased incidence of pneumonia, including serious pneumonia was observed with the use of FF/VI compared with VI monotherapy in two one-year-long exacerbation studies (study HZC102970 and study HZC102871). In addition, there were reports of fatal pneumonia in the FF/VI 200/25 treatment group.

In previous studies within the same class of medicines, there was approximately a 1.5 to 2-fold increase in the risk of serious pneumonia, the ICS-containing medication as compared to long-acting beta-agonist (LABA) monotherapy (30 vs. 55 pneumonia episodes per 1,000 person years for 500/50 fluticasone propionate / salmeterol combination [SFC] and 50 salmeterol, respectively [Crim, 2009]. There was no increase in the risk of pneumonia fatality, and results suggested a reduction in mortality in patients taking FSC relative to placebo, but did not achieve statistical significance [Calverley, 2007]. A similar two-fold increase was seen in the two, one-year long studies of FSC vs. SAL studies (data not shown).

In the FF/VI development program, the risk of serious pneumonia was almost three-fold greater for the FF/VI relative to the VI treatment groups (34.9, 37.0, and 33.6 per 1,000 person years for 50/250, 100/25, and 200/25 FF/VI versus 12.1 per 1,000 person years in 25 VI). In addition, inconsistencies in incidence of fatal pneumonia events between the two FF/VI exacerbation studies were noted; however, the low absolute number of fatal events precludes an accurate assessment of the risk or an evaluation of a dose response relationship due to low precision.

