J16.8	Pneumonia due to other specified infectious		
	organisms	4	0
J18.8	Other pneumonia, organism unspecified	4	0
J10.1	Influenza with oth resp manifest influenza virus identified	4	0
J15.6	Pneumonia due to other aerobic Gram-negative bacteria	3	0
J15.7	Pneumonia due to Mycoplasma pneumoniae	3	0
J17.3	Pneumonia in parasitic diseases	3	0
J15.4	Pneumonia due to other streptococci	2	0
J11.1	Influenza with oth resp manifestation virus not		
	identified	1	0
J11.0	Influenza with pneumonia, virus not identified	1	0
J15.9	Bacterial pneumonia, unspecified	1	0
J15.8	Other bacterial pneumonia	1	0
J15.5	Pneumonia due to Escherichia coli	1	0

Following the preliminary feasibility, subsequent feasibility on the total number of new users was evaluated as described in the protocol and presented in Table 4. This addressed the overlap between CPRD-GOLD and HES and definition of pneumonia episodes. The total number of pneumonia episodes available for the final analysis (e.g., time to first) are described in Table 4, including 283 pneumonia and 106 severe CAP, and 1 HAP. Based on concerns about statistical precision, the protocol analyses were adjusted prior to implementation of analysis.

Pneumonia Events	Year o	f Coho	ort Enti	ry						Total New Users
	2002	2003	2004	2005	2006	2007	2008	2009	2010	
Type of Pneumonia episode										
HAP							1			1
Severe CAP	16	22	13	11	18	7	11	5	3	106
Non-severe CAP	18	23	23	26	23	18	23	17	5	176
All Pneumonia	34	45	36	37	41	25	35	22	8	283

Table 4Count of First Pneumonia Events Including Adjustments for
Episodes: New User Cohort

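### Section 5.7.8: the severe-pneumonia power scenario conflicts with the pooled rate and event count it starts from, and the exclusion margins are stated without the condition (true hazard ratio near 1) on which they depend

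*Protocol*

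**What the plan says.** Section 5.7.8 of the Protocol describes 12,000 ICS and 6,600 LABD new users with 283 first pneumonia events, 106 of them severe. Section 5.4.1 gives the counts as "including 283 pneumonia and 106 severe CAP, and 1 HAP", so HAP and severe CAP combined, the primary outcome, come to 107.

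From these counts Section 5.7.8 concludes that "this study should be able to exclude a margin of 2.0 for severe pneumonia and 1.5 for overall pneumonia". It names neither the true ratio assumed nor the probability of success.

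The pooled rates are given as "15.8 per 1000 PY for CAP, 5.3 per 1000 person years for severe CAP". The severe power statement keeps 5.3 as its premise and adds a condition: "if the rate of severe pneumonia is 4 per 1000 PY in the LABD control arm", then "an odds ratio of 1.85 could be detected assuming a two-sided test at the 0.05 significance level with 82% power". The text adds: "This would require a rate of 7.4 per 1000 PY in the ICS-containing group for a total of 115 pneumonia events". For overall pneumonia it gives 85% power for an odds ratio of 1.5, from 11 against 16.4 per 1000 PY and 270 events.

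As background, Section 1 reports from earlier studies in the class "approximately a 1.5 to 2-fold increase in the risk of serious pneumonia".

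**The concern.** Three things do not fit together.

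- The severe scenario gives a pooled rate and two arm rates that cannot all be true with the stated group sizes. It also uses more severe events than this retrospective cohort contains.
- The two pooled rates, divided into their event counts, give different person-time. Yet Sections 5.7.2 and 5.7.4 end follow-up at the first pneumonia for both outcomes.
- The margin sentence reads as a property of the study, whereas the chance of excluding a margin depends strongly on the true ratio.

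The amendment was written to improve precision, and Section 3 says the results go to the FDA and EMA. A reader who takes the margin sentence at face value could see an upper limit above 2.0 as a surprise. It would in fact be the likely result if the true ratio were of the size that Section 1 cites.

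**Working it through.** **Inputs.** From Section 5.7.8: 12,000 ICS and 6,600 LABD users (ICS share a = 12,000/18,600 = 0.645), 106 severe and 283 total events, severe rates 4 and 7.4, overall rates 11 and 16.4, pooled rates 5.3 and 15.8 (all per 1000 PY), two-sided 0.05. From Section 5.4.1: one HAP, so 107 severe events. Assumption: about 1 PY per patient. The protocol does not state this, but it is the value that returns the protocol's event totals.

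**1. Reproducing the stated power.** Two-proportion test with pooled variance under the null and no continuity correction: power = Φ[(p1 − p0 − 1.96·SE0)/SE1].

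- Severe: events = 6.6×4 + 12×7.4 = 115.2. SE0 = 0.001202, SE1 = 0.001103. Power = Φ[(0.0034 − 0.002357)/0.001103] = 82.8% (stated 82%).
- Overall: events = 6.6×11 + 12×16.4 = 269.4. Power = 85.2% (stated 85%).

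Both figures follow from the arm rates printed beside them.

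**2. Severe arm rates against the pooled rate.** 115.2/18.6 = 6.19 per 1000 PY, not 5.3. Two ways to restore consistency:

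- Keep LABD 4 and pooled 5.3: ICS = (5.3×18.6 − 4×6.6)/12 = 6.0, ratio 1.50, 98.6 events, power about 44%.
- Keep the ratio at 1.85:

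| Events | LABD / ICS rate | Two-proportion power |
|---|---|---|
| 98.6 (pooled 5.3) | 3.42 / 6.33 | 76% |
| 106 | 3.68 / 6.81 | 79% |
| 107 | 3.72 / 6.87 | 80% |

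Schoenfeld, Φ[ln(1.85)·√(d·a·(1−a)) − 1.96], gives 88% at 115 events and 86% at 106 or 107.

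The 44% depends on which pooled rate is right. With 106 events at 1 PY each the pooled rate is 106/18.6 = 5.70. LABD 4 then gives ICS 6.63, ratio 1.66 and power 64%.

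**3. Person-time.** 283/0.0158 = 17,911 PY, and 106/0.0053 = 20,000 PY. Rounding does not close the gap: rates of 15.75 to 15.85 give 17,855 to 17,968 PY, and rates of 5.25 to 5.35 give 19,813 to 20,190 PY.

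**4. Margins.** P(upper 95% limit < M) = Φ[ln(M/HR)/SE − 1.96], with SE = 1/√(d·f·(1−f)) and f = a·HR/(a·HR + 1 − a), the ICS share of events. Example for severe pneumonia at HR 1.5: f = 0.732, SE = 0.218, Φ(0.288/0.218 − 1.96) = Φ(−0.64) = 26%.

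| True HR | Exclude 2.0, severe (d = 107) | Exclude 1.5, overall (d = 283) |
|---|---|---|
| 1.0 | 93% | 90% |
| 1.2 | 69% | 41% |
| 1.5 | 26% | 2.5% |
| 2.0 | 2.5% | below 0.01% |

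With the SE fixed at its HR = 1 value (0.202 and 0.124), the observed HR must be below about 2.0/exp(1.96×0.202) = 1.35 to exclude 2.0, and below about 1.5/exp(1.96×0.124) = 1.18 to exclude 1.5.

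**The case against.** A reader might infer that the stated power and margins are miscalculated. The documents do not support that: 82% and 85% both reproduce within a point, and the margins follow with about 90% probability or better when the true ratio is 1.

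The severe scenario is also conditional. The 115 events are what that alternative would generate, and Section 5.7.8 gives the actual 106 itself. At a ratio of 1.85 the loss is only a few points, and Schoenfeld, which suits the planned Cox model, stays above 82%. The 44% is power at a different ratio, so it does not replace the 82%. The overall scenario errs in the cautious direction: its arm rates pool to 269.4/18.6 = 14.5 against 15.8, and it needs 270 events where 283 exist. All of this stands. It limits the size of the point but does not reconcile 5.3 with 4 and 7.4.

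A second tempting reading is that the protocol expects a 1.5 to 2-fold effect and so contradicts its own margins. Section 1 reports that ratio from earlier studies and does not adopt it for this cohort, which also includes ICS monotherapy and several dose strengths. Nor is it contradictory to power for 1.5 and to speak of excluding 1.5: the first supposes that 1.5 is true, the second that the ratio is near 1. What remains is that the second supposition is not written down.

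A third is that weighting, or LABD time lost when ICS is started, cuts precision by a known amount. The protocol gives no weights from which to compute a variance increase. Section 5.7.8 bases its precision on events before censoring, and Section 5.7.2 lists ICS initiation as a censoring event, so the counts appear to reflect it already.

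Finally, no decision rule rests on the margins, and Section 5.7.2 judges precision by the width of the actual interval. That lowers the severity.

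**Conclusion.** The point holds, at moderate severity. Section 5.7.8 contains an internal conflict in the severe scenario (pooled rate 6.2 against 5.3, and 115 events against 106 to 107), an unexplained person-time difference of about 2,100 PY, and a margin claim that omits its condition.

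The margin claim matters most. It is sound at a true ratio of 1 and weakens quickly above it. At 1.5, the lower end of the range reported in the earlier class studies, the chance of excluding 2.0 is about one in four.

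The power conflict is minor if 1.85 is the ratio of interest. It is large only if LABD 4 and pooled 5.3 are taken as the premise. The power figures rest on the 1 PY assumption. The exclusion probabilities rest only on event counts, the group split and an unweighted log-hazard-ratio approximation, so the person-time mismatch does not alter them.

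**What to change.** Restate Section 5.7.8 as follows.

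- Use the fixed counts throughout: 107 severe and 283 total first events.
- Reconcile the person-time to one figure and recompute both pooled rates from it.
- Choose severe arm rates that pool to the observed rate, restate the severe power and name the method. Before weighting, at a ratio of 1.85 and 106 to 107 events, that is 79% to 80% by two proportions or about 86% by Schoenfeld.
- Replace the unconditional margin sentence with the probability of excluding 2.0 (severe) and 1.5 (overall) at true hazard ratios of 1.0, 1.2, 1.5 and 2.0, and say that exclusion is likely only if the true ratio is near 1.

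The cost is some rewording and one small table. The stated precision will look less favourable; the cohort, data and analyses do not change.

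### Section 5.7.8: the severe-pneumonia power scenario implies a pooled rate of about 6.2 per 1000 PY and 115 events, against the 5.3 it assumes and the 107 severe events already counted

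*Protocol*

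**What the plan says.** Protocol section 5.7.8 describes a cohort of "12,000 ICS-containing medication users and 6,600 LABD users" and puts its first events at 283, of which 106 are severe. For the severe outcome it starts from a pooled rate: "Assuming 5.3 per 1000 PY for severe CAP in the overall new user cohort". The LABD arm is then given a severe rate of 4 per 1000 PY, and the claim made for the study is that "an odds ratio of 1.85 could be detected" at a two-sided 0.05 level and 82% power. A remark in parentheses adds: "This would require a rate of 7.4 per 1000 PY in the ICS-containing group for a total of 115 pneumonia events".

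Section 5.4.1 gives the feasibility count of first events as "including 283 pneumonia and 106 severe CAP, and 1 HAP", and Table 4 shows the same totals. Section 5.7.4 makes HAP and severe CAP combined the primary outcome, so the count that matters is 106 + 1 = 107.

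**The concern.** One sentence carries three severe-event rates: 5.3 overall, 4 in LABD and 7.4 in ICS. Given the group sizes in the same section, they cannot all hold. The event total attached to the scenario is also larger than the number of events that exist. In a prospective study a planning scenario may exceed what is later observed. Here the events were counted before the paragraph was written, and further exclusions (ongoing pneumonia at entry, trimming of propensity scores) can only reduce them.

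This is the only power statement for the primary outcome, and section 3 says the results go to regulators. What is at stake is whether the stated sensitivity describes the cohort in hand.

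**Working it through.** **Inputs.** From 5.7.8: 12,000 ICS users, 6,600 LABD users, rates of 4 and 7.4 per 1000 PY, ratio 1.85, two-sided 0.05, 82% power, 115 events, pooled severe rate 5.3. From 5.4.1 and Table 4: 106 + 1 = 107 severe events. The protocol does not name its power formula or the person-time used. I assume about one person-year per user, because that reproduces its figures.

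**1. Reproduce the stated figure.** Two-proportion test, pooled variance under the null:

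power = Φ[(|p1 − p0| − 1.96·SE0) / SE1], where SE0 = √(p̄(1 − p̄)(1/n0 + 1/n1)) and SE1 = √(p0(1 − p0)/n0 + p1(1 − p1)/n1).

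- p0 = 0.004, p1 = 0.0074, n0 = 6,600, n1 = 12,000.
- SE0 = 0.0012023, SE1 = 0.0011026.
- (0.0034 − 0.0023565)/0.0011026 = 0.946, so power = 82.8%.
- Events: 6.6 × 4 + 12 × 7.4 = 26.4 + 88.8 = 115.2.

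Both stated figures (82%, 115) reproduce. The 5.3 does not enter the calculation.

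**2. Check the pooled rate.** 115.2/18.6 = 6.19 per 1000 PY, against the assumed 5.3. Unequal follow-up does not explain the gap: for 4 and 7.4 to pool to 5.3, the ICS share of person-time would have to be (5.3 − 4)/(7.4 − 4) = 38%, while ICS users are 12,000/18,600 = 64.5% of the cohort.

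**3. Same method on the 107 events, ratio 1.85.**

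- p0 = 107/(6,600 + 1.85 × 12,000) = 107/28,800 = 0.003715; p1 = 1.85 × p0 = 0.006873.
- SE0 = 0.0011590, SE1 = 0.0010629.
- (0.0031580 − 0.0022716)/0.0010629 = 0.834, so power = 79.8%.
- With 106 events: 79.4%.

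Solving the same formula for the ratio at 107 events gives 1.85 at 80% power and 1.89 at 82%.

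**4. Person-time.** 107 events over 18,600 PY is 5.75 per 1000 PY. To have 107 events at a pooled 5.3 takes 107/0.0053 ≈ 20,189 PY. Split 64.5 : 35.5, a ratio of 1.85 then means 3.42 (LABD) and 6.33 (ICS) per 1000 PY, and power is again 79.8%. The event count drives the answer; the choice of person-time hardly matters.

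**5. Schoenfeld's formula, closer to the planned Cox model.** power = Φ[√(E·q(1 − q))·ln(HR) − 1.96], with q = 0.645 and q(1 − q) = 0.2289.

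- E = 107, HR = 1.85: √(107 × 0.2289) × 0.6152 − 1.96 = 1.085, so power = 86.1%.
- Events needed for 82%: (1.96 + 0.915)²/(0.2289 × 0.6152²) = 95.4, i.e. 96.

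Neither result allows for loss of precision from inverse-probability weighting.

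**6. Companion scenario.** For all pneumonia, 11 versus 16.4 per 1000 PY gives 6.6 × 11 + 12 × 16.4 = 269.4 events (stated 270), a pooled rate of 14.5 and 85% power. These lie within the feasibility totals of 283 events and 15.8. Only the severe scenario exceeds its own data.

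**The case against.** The best defence is that 7.4 is not an estimate. It is 4 × 1.85, the rate an effect would need in order to be detectable, and the power follows correctly from it. That stands. It also rules out two stronger readings that a reader might infer.

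- *That the ICS rate should be 6.0 and the ratio 1.5.* A LABD rate of 4 with 5.3 overall does imply (5.3 × 18.6 − 4 × 6.6)/12 = 6.0 in ICS. But a detectable alternative need not equal the contrast implied by pooled data, so 6.0 is not a corrected 7.4.
- *That the true power is 44%, so the study would probably miss its effect.* 44% is the two-proportion power at a ratio of 1.5, for which the protocol claims no power in severe pneumonia. Schoenfeld's formula with 107 events gives about 52% there, so even the direction of that statement depends on the method.

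A figure of 76% at ratio 1.85 can also be obtained by applying 5.3 to 18,600 PY. That uses about 99 events when 107 are known.

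The defence can add that the section's leading claim, that a margin of 2.0 can be excluded for severe pneumonia, is tied to the 106 observed events. With a true ratio of 1, the upper 95% limit would be about exp(1.96/√(106 × 0.2289)) = 1.49. That claim is untouched. Finally, the cohort size is fixed, so no design decision changes. All of this limits the size of the point. None of it reconciles 6.2 with 5.3, or 115 with 107.

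**Conclusion.** The inconsistency is real and its effect is modest. The scenario assumes a pooled severe rate of 5.3 but implies about 6.2, and it rests on 115 events where 107 exist. By the protocol's own apparent method, power at a ratio of 1.85 is about 80% rather than 82%, and the ratio detectable at 82% is about 1.89. That 82% needs 115 events is true only of the two-proportion scenario; by Schoenfeld's formula 96 suffice, and 107 give about 86%.

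These figures assume the 64.5 : 35.5 split applies to person-time, that all 107 events survive into the final analysis population, and that weighting costs no precision. If events are lost or the weights are variable, power falls below the figures given here.

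**What to change.** Rewrite the severe-pneumonia scenario in 5.7.8 on the 107 events in hand:

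- Use arm rates that pool to the feasibility rate, and state the person-time. For a ratio of 1.85 at a pooled 5.3, these are about 3.4 and 6.3 per 1000 PY over roughly 20,200 PY.
- Give the detectable ratio as about 1.85 at 80% power or about 1.89 at 82%, and name the formula. If Schoenfeld's formula is preferred, report about 86% at 1.85 and say that it precedes any loss from weighting.
- Delete the 115-event figure.
- Optionally, add as context that a LABD rate of 4 with a pooled 5.3 corresponds to a ratio of about 1.5, where power is about 44% (two-proportion) to 52% (Schoenfeld). Section 1 cites a 1.5 to 2-fold increase for the class, so readers may want this. It should not be presented as a correction of the 82%.

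The cost is one paragraph. Cohort, outcome definitions and analysis are unchanged; by the two-proportion method the stated power becomes slightly less favourable.
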